**8.8 Fat and Muscle Biopsies and Analysis:**

**9. STATISTICAL ANALYSIS**

**10. STUDY TEAM**

## METABOLIC CHARACTERISTICS OF LEAN DIABETES IN RURAL AND SEMI-URBAN INDIA AND IN THE UNITED STATES.

### 1 INTRODUCTION

#### BASIC INFORMATION:

##### 1.1 THERAPEUTIC AREA:

India has the world's highest prevalence of diabetes, expected to rise to 80 million by 2030. This includes many patients with lean diabetes, with low body mass index (BMI) and severe complications of diabetes. Despite its prevalence in India and other countries and its dire health consequences to individuals with the disease, little is known about the aetiopathogenesis and the genotype-phenotype relationship, lean diabetes being a cluster of low birth weight individuals, MODY, lipodystrophic disease, type 1 diabetes and fibrocalcific disease. While rudimentary tests have suggested defects in both insulin secretion and action, no comprehensive metabolic studies have been performed. It is therefore unclear as to how these patients should be treated. The optimal therapeutic adjunct whether a suitable oral antidiabetic agent or insulin is not yet determined. Defining the metabolic defects of 'lean' diabetes should have tremendous therapeutic benefit for millions of patients with this elusive condition.

##### 1.2 BACKGROUND AND SIGNIFICANCE:

###### 1.2. Significance of Diabetes in Indian population and South Asians living in the United States:

Diabetes is rapidly becoming a global epidemic. India has the world's highest prevalence of diabetes, expected to rise to 80 million by 2030 (1). As a consequence of rapid Westernization, many Indians are developing type 2 diabetes (T2DM). Of note, T2DM incidence in Indians rises sharply when body mass index (BMI) rises above 22 kg/m^2 (2).

Additionally, the diabetes population in India and other LMICs includes many patients with low BMI and severe complications of diabetes. Various reports suggest that these patients are surprisingly insulin resistant considering their lean body habitus. Some of these individuals have Fibrocalculous Pancreatic Diabetes (FCPD), in whom pancreatic calculi and/or ductal dilatation may contribute to the etiology of their disease (3). Many, however, are classified as **Lean Diabetes**, identified clinically by early onset, high insulin requirements, absence of pancreatic calculi or ductal dilation, and low BMI (typically  $\leq 17\text{kg/m}^2$  at presentation). The majority of young adults with diabetes in India are likely to have FCPD or lean diabetes (3). Both conditions differ from type 1 diabetes by persistent C-peptide response to nutrient stimuli, and absence of ketosis and pancreatic beta cell autoimmunity markers (4). Lean diabetes tends to present in young adults between the ages of 20 and 40 and afflicts men and women at a 2:1 ratio. Despite its sizeable prevalence, lean diabetes remains a relatively unknown disease that stirs conflicting opinions regarding its classification, diagnostic criteria, and pathogenesis (5). Of note, patients with lean diabetes appear to have elevated VLDL and triglycerides as well as insulin resistance based on insulin tolerance tests (6).

It has increasingly become apparent that marked ethnic variability in the clinical features of diabetes exists. Variability in the prevalence and pattern of disease among ethnic groups

can be secondary to both genetic and environmental modifying factors. South Asians in the United States have a higher prevalence of diabetes than non-Hispanic whites, despite lower BMI and being younger in age (7). Studies in the United Kingdom have shown that migrant Indians have increased insulin resistance and hyperinsulinemia compared to Europeans (8). However, comprehensive metabolic studies of these individuals are lacking in the United States. *Careful metabolic 'phenotyping' and genotyping of South Asian individuals with lean diabetes would be very helpful to better understand this condition and develop appropriate therapeutic approaches.* Our study aims to define the ethnic variability in clinical and metabolic characteristics of diabetes in South Asian population living in United States.

**Insulin resistance in individuals with lean diabetes:** There are currently very few publications on the entity known as 'lean' or 'malnutrition' diabetes. Numerous case reports, however have described a high degree of insulin resistance in some of these individuals (7, 8). Nonetheless, there is a debate to whether the mechanisms are attributable to the pancreatic beta-cell, skeletal muscle, adipose tissue, or other tissues.

### **1.2.2 Significance of fat mass in the etiology of insulin resistance:**

It is a well-recognized yet intriguing concept that individuals at both ends of the weight spectrum have abnormal fat metabolism impacting insulin sensitivity. In obesity, increased fat mass promotes fatty acid flux to nonadipose tissues (9). In apparent contradiction, similar metabolic features are observed in lipodystrophy, including insulin resistance, hepatic steatosis, hyperlipidemia and diabetes (10). In both obesity and lipodystrophy, a storage defect within adipocytes (due either to engorgement with lipid or a paucity of adipocytes) leads to excess accumulation of triglyceride in non-adipose tissues. Increased free fatty acid (FFA) availability in both conditions inhibits the effects of insulin on hepatic and peripheral glucose metabolism (11,12). Indeed, systemic insulin resistance is associated with increased adipose tissue lipolysis and resistance to the anti-lipolytic effects of insulin (13,14). Increased hepatic fat content is receiving particular attention as a potential causative factor of insulin resistance (15). In addition to the well-established associations between IHTG and hepatic insulin resistance (16), our preliminary data (below) demonstrate an intriguing association with peripheral insulin resistance. *Based upon the relationships described above, we hypothesize that deficient fat stores in individuals with lean diabetes may promote hepatic triglyceride storage, leading to elevated circulating fatty acids and insulin resistance.*

### **1.3 SIGNIFICANCE:**

It is highly intriguing, in the twenty-first century, to encounter a condition as prevalent as lean diabetes yet about which so much remains to be learned. The diabetes literature is dominated by studies conducted in high income countries, where this condition is never encountered. *These would be the first truly comprehensive studies defining the body composition and metabolic features of lean diabetes.* Scientifically, this application will explore a novel frontier in the intriguing dynamic between fat metabolism and insulin sensitivity.

**Clinical relevance:** Given India's high prevalence of diabetes, of which a substantial yet poorly defined proportion is likely to have lean diabetes, this proposal would have considerable clinical relevance for India and many other countries. In the absence of

sufficient information about this condition and its management, many lean diabetes patients are labeled as type 1 diabetes and are prescribed insulin. Unfortunately, inconsistent food availability among poor patients results in many insulin-induced hypoglycemic deaths. A better understanding of the metabolic defects of this condition should be very helpful in pointing towards more appropriate therapeutic approaches. Specifically, being able to clearly demonstrate that these subjects are insulin resistant would favor the use of safer, cheaper oral insulin sensitizing agents. This application therefore seeks to shift current clinical practice paradigms for underweight patients with diabetes, by studying a novel hypothesis concerning the pathophysiology of lean diabetes. *Defining the metabolic defects of lean diabetes could therefore have tremendous therapeutic benefit for millions of patients with this elusive condition.*

#### **1.4 PRELIMINARY STUDIES**

**Moderate elevations in FFA levels characteristic of T2DM impair glucose effectiveness:** *These studies were performed at Einstein, and highlight the impact of abnormal fatty acid flux on glucose metabolism.* In previously reported studies, FFA levels were elevated in poorly controlled T2DM subjects ( $377 \pm 46$  mM) during glucose clamp studies, relative to age- and BMI-matched nondiabetic subjects ( $167 \pm 12$  mM). To determine the extent to which the ~2-fold elevations in FFA characteristic of poorly controlled T2DM contribute to defects in glucose metabolism, we infused nicotinic acid at 0.015 mg/kg.min to lower FFA to nondiabetic levels in n=9 poorly controlled T2DM subjects ( $\text{HbA}_{1\text{C}} = 10 \pm 1\%$ , age =  $49 \pm 3$  yr; BMI =  $27 \pm 1$  kg/m^2). We established steady state hormone and tracer conditions over the first four hours at normoglycemic glucose levels (90 mg/dl) and then abruptly raised glucose levels to 180 mg/dl for the final 2 hours of the studies. Normalizing FFA levels essentially restored the endogenous glucose production (EGP) response to hyperglycemia. Indeed, EGP was reduced by  $41 \pm 8\%$  with the onset of hyperglycemia when FFA were lowered with nicotinic acid ( $p < 0.001$ ), which was comparable to the response in nondiabetic individuals. *These data indicate that moderately increased FFA levels could contribute substantially to abnormal glucose metabolism in T2DM.*

**Increased Intrahepatic Triglyceride (IHTG) Is Associated with Peripheral Insulin Resistance:** *These studies were performed at Einstein.* A total of 56 nondiabetic subjects (49 M) ranging in age from 19 to 78 yrs underwent five hour hyperinsulinemic (40 mU/m^2.min), euglycemic (90 mg/dl) 'clamp' studies, using H-glucose to quantify insulin-mediated glucose uptake. Mean glucose uptake was  $10.2 \pm 0.4$  mg/kg.min among normal weight subjects (BMI < 25; n=15) vs.  $8.0 \pm 0.8$  mg/kg.min in overweight-to-obese subjects (BMI > 25; n=41; ~22% reduction,  $p < 0.001$ ), with a significant, inverse correlation between BMI and glucose uptake ( $r = -0.386$ ,  $p = 0.004$ ). As noted above, *altered fat deposition may contribute to insulin resistance in humans.* Since visceral (VF) and deep subcutaneous fat (SF) depots may contribute to IHTG via hepatic delivery of free fatty acids (FFA), we simultaneously measured intramyocellular lipid (IMCL), IHTG, VF and abdominal SF in a subgroup of n=12 nondiabetic, nonobese individuals using noninvasive H magnetic resonance spectroscopy (MRS) and magnetic resonance imaging (MRI). Positive correlations were observed among IMCL, IHTG and VF. There were remarkably tight correlations between IHTG and peripheral (non-hepatic) insulin sensitivity ( $r = -0.87$ ,  $p < 0.001$ ). Intriguingly, however, there was a lack of correlation of insulin-stimulated glucose uptake with IMCL or other fat depots. These observations are consistent with studies in rodents in which decreasing IHTG levels improved muscle insulin action. Although the IHTG levels in these nonobese subjects were substantially lower than levels

reported in obesity and T2DM, the inverse correlation of IHTG with insulin sensitivity was exceptionally tight. This was presumably aided by the sensitive measures generated by *in vivo* H MRS and insulin 'clamps'. *This association between IHTG and insulin resistance at normal body weights demonstrates that fatty acid flux and tissue triglyceride content are important determinants of insulin sensitivity, even in the absence of obesity.*

**Deleterious Metabolic Effects of Low Birth Weight:** *These studies were performed at Christian Medical College India (CMC) in collaboration with University of Copenhagen.* Nutrition in rural areas of India is still less than satisfactory. Hence, pregnant women often have insufficient protein intake, and the prevalence of low birth weight in India is endemic (26% of the babies born in rural India). These babies are more prone to diabetes in adulthood. A population-based cohort of 60 low birth weight (LBW) subjects and 60 normal birth weight (NBW) subjects, aged 18 to 22 years, was recruited from a rural area near Vellore. Insulin resistance was assessed by HOMA and by the glucose infusion rate required during hyperinsulinemic euglycaemic clamp studies (M-value). Body composition was measured by DEXA, and liver triglyceride content by MRS. Among these young subjects, with comparable BMI's in both groups ( $\sim 18$  kg/m^2), LBW was associated with a reduction in insulin sensitivity as assessed by HOMA (LBW=1.02 $\pm$ 0.13 vs. NBW=0.75 $\pm$ 0.10,  $p<0.05$ ) and lower total body fat content (LBW=7654 $\pm$ 642 vs. 8559 $\pm$ 542 g,  $p<0.05$ ). However, the M-value with this clamp technique was highly variable, and did not show a difference between groups. IHTG analysis is pending. *While these studies only included nondiabetic subjects, these data suggested a relationship between LBW and insulin resistance, consistent with the increased propensity for diabetes in malnourished individuals later in life.*

### **1.5 Relevance to Project:**

These data indicate that moderately increased FFA levels could contribute substantially to abnormal glucose metabolism in T2DM. The association between IHTG and insulin resistance at normal body weights demonstrates that fatty acid flux and tissue triglyceride content are important determinants of insulin sensitivity, even in the absence of obesity. While these studies only included nondiabetic subjects, these data suggested a relationship between LBW and insulin resistance, consistent with the increased propensity for diabetes in malnourished individuals later in life.

## **2.0 OBJECTIVES:**

### **2.1 Objective 1**

- (i) To characterize body composition and hepatic lipid deposition in individuals with lean diabetes.

### **2.2 Objective 2**

- (ii) To characterize insulin's ability to regulate glucose fluxes and inhibit lipolysis in individuals with lean diabetes.

### **2.3 Objective 3**

- (iii) To assess the insulin secretory response to meal challenge in individuals with lean diabetes

## 2.4 Objective 4

- (iv) To characterize and study the gene expression profile of adipose tissue and skeletal muscle in individuals with lean diabetes.

## 2.5 Objective 5

- (v) To understand the immunologic determinants of diabetes in the lean.

## 2.6 Objective 6

- (vi) To sequence the genes involved in monogenic forms of diabetes to identify the genetic variants and their association with lean diabetes

## 3.0 RATIONALE

### **3.1 RATIONALE FOR THE TRIAL FOR OBJECTIVE 1:**

*Of note, these studies aim to carefully characterize a condition about which little is known.* Since there are no rigorous definitions differentiating lean diabetes from T2DM, we will classify the DM subject groups based upon their BMI ranges. To further increase the likelihood of correctly identifying lean diabetes, we will elicit a history of low birth weight and documented malnutrition in the lean diabetes subjects. We will also carefully exclude subjects with features of type 1 diabetes, excluding individuals who test positive for anti-CAD, insulin and/or IC2 antibodies.

The lack of weight matching between the two DM groups is an inevitable feature of the different pathophysiology of these conditions. To minimize the impact of a sizeable difference in BMI, we will select a T2DM group at the lower BMI range for this condition. As noted above, risk of T2DM among ethnic Indians begins to increase sharply above a BMI of 22 kg/m^2.

To increase the likelihood that the “nondiabetic comparators” will have a normal metabolic profile, we will select subjects with normal birth weight and no documented history of malnutrition, despite having a BMI in the target range. Of note, it is possible that these individuals will also demonstrate some metabolic consequences of decreased fat mass. If we document insulin resistance in the underweight nondiabetic group, we will consider adding a fourth group of normal weight, nondiabetic subjects that would be BMI-matched to the T2DM group (BMI 22-25 kg/m^2).

DEXA scanning will quantify truncal fat and total body fat. If significant relationships are discovered between truncal fat content and metabolic endpoints, future studies will include a more comprehensive analysis of visceral vs. subcutaneous abdominal fat using CT scanning.

### **3.2 RATIONALE FOR THE TRIAL FOR OBJECTIVE 2:**

[name] and her research group have now performed more than eight hundred clamp studies in human subjects, and thus have considerable experience both in the execution of the studies and in data analysis. Indeed, the human liver is known to be exquisitely

sensitive to small changes in plasma insulin levels, such that small increases in insulin rapidly decrease glucose production yet have little effect on peripheral glucose uptake. Particular benefits of the proposed study design include the proposed *stepped insulin clamp studies* for measuring both hepatic and peripheral insulin action, and the pancreatic clamp study design to maintain stable hormone levels. The latter is particularly relevant to the low insulin phase of the study in which hepatic insulin action is determined.

Insulin will be infused overnight prior to the studies in both DM groups, to correct the confounding effects of glucose-induced insulin resistance. A variable low-dose infusion of insulin will be initiated at 10 pm, and will be adjusted overnight based upon hourly glucose measurements to attain plasma glucose concentrations of 100 - 120 mg/dl prior to the start of the clamp study. This will ensure that all subjects will be studied under normoglycemic conditions. *This gradual lowering of plasma glucose is intended to avoid activation of counter-regulatory responses.* Indeed, the phenomenon of 'glucose toxicity' is recognized to cause reversible resistance to insulin at the level of the liver, muscle and adipocyte (20).

*To what extent do increased FFA contribute to insulin resistance in the DM groups?* As described above, there is substantial evidence that increased FFA levels in T2DM and obesity contribute to insulin resistance. Response to insulin's anti-lipolytic effects will be explored in this proposal by following FFA levels during the stepped insulin clamp studies, with the hypothesis that defective fat storage in lean diabetes will increase FFA levels and contribute to insulin resistance.

It could be argued that the proposed measures of body composition and insulin sensitivity, while highly sensitive and 'state-of-the-art', will be observational and will not prove causality. However, given the tremendous need for more knowledge about lean diabetes, it is essential to first do a thorough 'metabolic phenotyping' of individuals with lean diabetes.

### **3.3 RATIONALE FOR THE TRIAL FOR OBJECTIVE 3:**

While rudimentary tests in individuals with lean diabetes have suggested defects in both insulin secretion and action, no comprehensive metabolic studies have been performed. It is therefore unclear as to how these patients should be treated.

### **3.4 RATIONALE FOR THE TRIAL FOR OBJECTIVE 4:**

It is a well-recognized yet intriguing concept that individuals at both ends of the weight spectrum have abnormal fat metabolism impacting insulin sensitivity. In obesity, increased fat mass promotes fatty acid flux to nonadipose tissues (21). In apparent contradiction, similar metabolic features are observed in lipodystrophy, including insulin resistance, hepatic steatosis, hyperlipidemia and diabetes (22). In both obesity and lipodystrophy, a storage defect within adipocytes (due either to engorgement with lipid or a paucity of adipocytes) leads to excess accumulation of triglyceride in non-adipose tissues. Increased free fatty acid (FFA) availability in both conditions inhibits the effects of insulin on hepatic and peripheral glucose metabolism (23,24). Indeed, systemic insulin resistance is associated with increased adipose tissue lipolysis and resistance to the anti-lipolytic effects of insulin (25,26). Increased hepatic fat content is receiving particular attention as a potential causative factor of insulin resistance (27). In addition to the well-established associations between IHTG and hepatic insulin resistance (28), our preliminary data (below) demonstrate an intriguing association with peripheral insulin resistance. *Based upon the relationships described above, we hypothesize that deficient fat stores in individuals with lean diabetes may promote hepatic triglyceride storage, leading to elevated circulating fatty acids and insulin resistance.*

## **4.0 OUTCOME**

### **4.1 OUTCOME OF OBJECTIVE 1:**

To define body composition (DEXA) and liver triglyceride content (MRI) as well as determine the presence of fibrocalcific pancreatic disease, in young adults who have lean diabetes, based upon a history of established diabetes and malnutrition, without features of type 1 diabetes.

### **4.2 OUTCOME OF OBJECTIVE 2:**

***Hepatic insulin action:*** this will be determined as the ability of low infusion rates of insulin ( $20 \text{ mU/m}^2.\text{min}$  above basal requirements) to suppress glucose production during the “low insulin phase” of the clamp studies.

***Peripheral insulin action:*** this will be determined as the ability of high infusion rates of insulin to stimulate glucose uptake during the “high insulin phase” of the clamp studies. For the final two hours of the study, insulin infusion rates will be raised by a larger increment ( $80 \text{ mU/m}^2.\text{min}$ ) above basal insulin requirements, to determine peripheral insulin sensitivity under maximally stimulated conditions.

***Glucose kinetics:*** Rates of glucose appearance (Ra) and disappearance (Rd) and other indices of glucose turnover will be estimated using Steele equations (). Endogenous glucose production will be determined by subtracting the rates of glucose infusion from the tracer-derived Ra.

***Plasma hormone and substrate determinations:*** plasma insulin, free-insulin, C-peptide, and glucagon concentrations will be measured by Core Analytical Lab at Albert Einstein College of Medicine (). Plasma lactate, FFA and glycerol concentrations will be measured using spectrophotometric or colorimetric techniques ().

***6-6 D-glucose determinations:*** Initially, it is likely that these determinations will be performed at Einstein. Plasma samples for Gas Chromatography-Mass Spectroscopy (GC-MS) will be derivatized after protein precipitation to the aldonitrile pentacetate with hydroxylamine hydrochloride-acetic anhydride. GC/electron impact-mass spectrometry analysis will be performed on an Agilent model 6890/5973 with a 7673 Agilent autosampler ().

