#### 8.4 Plasma measurements:

From t=0 to t= 360 min., blood samples will be obtained at hourly intervals for

determination of plasma glucose, insulin, glucagon, C-peptide, and Free fatty acids (FFA). Additional samples for D2G glucose determinations will also be obtained every 15 minutes.

Plasma glucose will be measured every 5-10 min to adjust the glucose infusion rate. Plasma lipids (LDL, HDL, VLDL, total Cholesterol and Triglycerides) will be measured at t=0).

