### **8.6 Substrate determination:**

Plasma FFA levels will be determined by using an acyl-CoA oxidase based colorimetric kit (Wako, Osaka, Japan) (99, 100). Plasma lactate will be measured by fluorometric enzyme techniques (101).

Plasma for labeled glucose will be treated as previously described (102). Rates of glucose appearance (Ra) and disappearance (Rd) and other indices of glucose turnover will be estimated by using the steady-state equation of Steele (103). Endogenous glucose production (EGP) will be determined by subtracting the rates of glucose infusion from the tracer-derived rate of appearance of glucose. Data for glucose turnover represent the mean values during the final 60 min of the low insulin period (t=60-120 min), and during the final 60 min of the high insulin period (t=180-240 min).

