## 9. STATISTICAL ANALYSIS

**Analysis of Variance (ANOVA):** A one-way ANOVA will be used to compare the primary measures (eg. glucose uptake, glucose production, IHTG) among the three study groups. When the ANOVA indicates a significant difference, unpaired t-tests will be performed to distinguish which groups differ. The null hypothesis is that the primary measures will not differ between the three groups: the nondiabetic, lean diabetes and T2DM groups. These analyses will be performed in collaboration with Einstein's biostatistician .

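### Hepatic insulin action is defined as suppression of glucose production, but the plan names no basal glucose production value or suppression measure, although the samples needed are already taken

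*Combined protocol and SAP*

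**What the plan says.** Section 4.2 introduces hepatic insulin action with "this will be determined as the ability of low infusion rates of insulin" and says that what insulin must do is "suppress glucose production during the" low-insulin phase. It gives no formula, no reference rate, and no choice between a percent and an absolute scale. EGP itself is defined: "Endogenous glucose production will be determined by subtracting the rates of glucose infusion from the tracer-derived Ra".

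Section 8.6 states which values are kept: "Data for glucose turnover represent the mean values during the final 60 min of the low insulin period (t=60-120 min") and the mean "during the final 60 min of the high insulin period (t=180-240 min"). No window is labelled basal.

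Section 9 states the comparison: "A one-way ANOVA will be used to compare the primary measures (eg. glucose uptake, glucose production, IHTG) among the three study groups". It mentions no change score, percent suppression or basal covariate.

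The design does include a basal phase. In section 8.3 the tracer starts at t=0 and runs for all six hours, and the first 120 minutes are used to find each subject's basal insulin requirement. Section 8.4 has blood drawn from t=0 to t=360 and adds: "Additional samples for D2G glucose determinations will also be obtained every 15 minutes".

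**The concern.** EGP in the low-insulin phase depends on two things: the rate the subject started from, and the fraction of it that insulin switches off. Only the second is insulin action as section 4.2 defines it. If groups differ in basal EGP, a comparison of low-phase EGP can show a hepatic defect where insulin works equally well, or hide a real one.

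The study has no randomisation to balance basal EGP. The BMI ranges also differ by design (16-22.5 kg/m² for lean diabetes and controls, 22.5-27 for type 2 diabetes), so a per-kg rate would carry a denominator that differs by group. Glucose production is one of the primary measures named in section 9, and hepatic action is one of the two clamp measures of insulin action in 4.2.

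Leaving the measure open also allows the choice between absolute and relative EGP to be made after the results are seen.

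**Working it through.** **1. The windows against the clock.** Section 8.3 gives basal 0-120, low 120-240 and high 240-360 min. It also says that the low-phase increase happens at T=0, which points to a second clock starting with the low phase. Section 8.6 can be read on either clock:

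| Window in 8.6 | Label in 8.6 | On the 0-360 clock | If t=0 is the start of the low phase |
|---|---|---|---|
| 60-120 | low | last hour of basal | last hour of low |
| 180-240 | high | last hour of low | last hour of high |
| Phase left without a summary | | high | basal |

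Three phases need three summaries. Two are given, and on neither clock do they cover all three phases. If the labels are right, there is no basal value. If the times are right, basal and low-phase means exist under the wrong labels and the high phase has none.

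**2. Can suppression be computed?** Yes. Sampling every 15 minutes puts samples at 60, 75, 90, 105 and 120 min, five in the last basal hour with the tracer running. Insulin in this phase is titrated to hold 90 mg/dl without exogenous glucose, so basal EGP is then simply the tracer-derived rate of appearance.

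**3. The plan's own sample size.** The power analysis gives 20 per group from glucose uptake of 8.0 (SD 2.0) v 10.2 (SD 2.5) mg/kg.min, difference 2.2, two-tailed t-test, at least 80% power. Alpha is not stated; I take 0.05. Root-mean-square SD = √((2.0² + 2.5²)/2) = 2.264. The t-test needs 18 per group, and power at 20 is 0.85, so the stated figure is adequate. It concerns glucose uptake and says nothing about EGP.

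**4. What a basal difference does (assumed values).** The documents give no basal EGP and no unit for it. I assume 2.0-2.4 mg/kg.min, taking the unit from glucose uptake. Low-phase EGP = basal × (1 − suppression).

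- Equal suppression of 50%: 2.0 × 0.50 = 1.0 and 2.4 × 0.50 = 1.2. Apparent difference 0.2/1.0 = 20%, with none in suppression.
- Unequal suppression of 52% v 60%: 2.0 × 0.48 = 0.96 and 2.4 × 0.40 = 0.96. A real difference vanishes. These figures were chosen to cancel exactly.

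**5. How often this would be declared significant.** Suppression is identical, with 20 per group and a two-sided t-test at 0.05 on low-phase EGP. The coefficient of variation (CV) is assumed. The first figure sets the SD from the lower group for both groups; the second applies the CV to each group's own mean.

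| Basal difference | CV 20% | CV 30% | CV 40% |
|---|---|---|---|
| 10% | 0.34 / 0.31 | 0.18 / 0.17 | 0.12 / 0.11 |
| 20% | 0.87 / 0.80 | 0.54 / 0.46 | 0.34 / 0.29 |

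All exceed 0.05, the rate wanted when suppression is equal.

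**6. Precision of the alternatives.** At 20 per group and 80% power, the detectable difference in low-phase EGP is 0.91 SD. With equal SDs and basal-to-low correlation r, the SD is multiplied by √(2(1−r)) for a change score and by √(1−r²) for low-phase EGP adjusted for basal. At r = 0.3, 0.5 and 0.7 the detectable differences are 1.08, 0.91 and 0.70 SD for change, and 0.87, 0.79 and 0.65 SD for adjustment. The documents do not give r.

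**The case against.** The strongest reply is that section 4.2 already says suppression, so glucose production in section 9 is shorthand for that outcome; section 9 lists its measures only as examples and never says absolute. This is fair as far as it goes. Comparison of absolute low-phase EGP is the natural reading of 8.6 and 9 together, but the text does not state it.

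A second reply is that the design limits baseline differences: overnight insulin normalises glucose in the diabetes groups (section 3.2), basal insulin is titrated individually, and the low rate is an increment above each subject's basal requirement. These steps bring groups to a similar glucose level. They do not make basal EGP equal, and the documents offer no evidence either way.

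Third, on the 0-360 clock the 60-120 window is the basal hour, so the basal mean may be present but mislabelled. That stands, and so the missing basal value cannot be judged separately from the clock conflict. It does not rescue the plan: on that reading the high phase loses its summary, and still no suppression measure is defined.

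A reader might also infer that suppression cannot be computed at all. The documents do not support this, since tracer and sampling cover the basal phase. What is missing is a specification.

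**Conclusion.** The point holds as a gap between the outcome definition and the analysis. Section 4.2 promises suppression; 8.6 names no basal summary; 9 makes no reference to basal. As written, the hepatic comparison is open to confounding by any group difference in basal EGP, while a baseline value the study already collects goes unused. The sponsor's own preliminary work (section 1.4) reported the EGP response to hyperglycemia as a percent reduction, so a baseline-referenced measure is familiar ground.

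The size is unknown. The 20% apparent difference and the 0.11 to 0.87 range of spurious significance rest wholly on assumed basal rates, CVs and a per-kg scale. They show what could happen; a reader should not take them as evidence that the groups differ in basal EGP or that the result will be biased by that amount. The change is worth making before analysis because it costs little and fixes the choice of measure in advance.

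**What to change.** - **Section 8.6:** define basal, low and high windows on one clock and reconcile them with 8.3 and 8.4. Put the basal window late in the basal phase and state the minimum number of tracer samples. On the 0-360 clock, the last 30 minutes hold three samples (90, 105, 120) and the last hour five.
- **Sections 4.2 and 9:** make the hepatic outcome baseline-referenced and name one measure as primary. Either percent suppression, 100 × (basal EGP − low-phase EGP)/basal EGP, or low-phase EGP adjusted for basal EGP would do. Percent suppression cancels the body-size denominator. Adjustment detects smaller differences than a change score at each correlation tried above, but noise in basal EGP can leave part of a baseline difference uncorrected.
- **Reporting:** show basal and low-phase absolute EGP by group beside the primary measure, and state the unit.

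The cost is wording in three sections, with no new samples or procedures. The downside is some noise from the basal estimate: insulin is still being adjusted about every 20-25 minutes in that phase, while 8.6 relies on a steady-state equation. That is the reason for a late window and for keeping the absolute values in the report.
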